6.1.2.4. General Considerations for the PTFU Period

For the safety analyses during the PTFU period, baseline is defined as the last nonmissing assessment on or prior to entering the PTFU period, that is, on or prior to Week 104 (Visit 29), or ETV.

Safety data will be summarized using descriptive statistics without inferential statistics by the study treatment the patient was receiving immediately prior to entering PTFU period.

6.2. Adjustments for Covariates

There are no adjustments for covariates.

6.3. Handling of Dropouts or Missing Data

6.3.1. Non-Responder Imputation for Clinical Response

The NRI method may be used to address missingness when the estimand of interest uses the composite strategy for handling intercurrent events.

Analysis of categorical efficacy and health outcome variables will be assessed using a NRI method. Patients will be considered non-responders for the NRI analysis if they do not meet the clinical response criteria or have missing clinical response data at the analysis time point of interest. All nonresponders at Week 16 (Visit 8), as well as all patients who discontinue study treatment at any time prior to Week 16 for any reason, will be defined as non-responders for the

NRI analysis at Week 16. For the OLE Period Population, all non-responders at Week 104 (Visit 29), as well as patients who discontinue the originally assigned study treatment at any time prior to Week 104 for any reason, will be defined as non-responders for the NRI analysis at Week 104. For the Switcher population, all non-responders at Week 104 (Visit 29), as well as patients who discontinue ixekizumab after the switch at any time prior to Week 104 for any reason, will be defined as non-responders for the Week 104 analysis.

The NRI will be applied at any time point specified for analysis.

6.3.2. *Last Observation Carried Forward*

When last observation carried forward (LOCF) is applied, the last nonmissing postbaseline observation on or prior to the missed visit within the same period will be carried forward to subsequent time points for evaluation. Patients without at least 1 postbaseline observation will not be included for evaluation. This method will be used to handle missing data for individual components of a composite endpoint, such as JIA ACR or Disease Flare. Further details are described in [Appendix 1](#) and [Appendix 2](#).

6.3.3. *Modified Baseline Observation Carried Forward*

A complete guideline on statistical principles for clinical trials such as impact on trial design, conduct, and analysis, and documenting estimands and sensitivity analysis can be found in the *ICH E9 Statistical Principles for Clinical Trials* and the *addendum (R1)* (EMA 2020).

The mBOCF method is based on an estimand that handles the intercurrent event of discontinuing study drug due to an AE by defining the participant as not receiving any benefit from study drug after the event. That is the participant is defined as reverting back to baseline regardless of any continuing efficacy benefits they may still have received after the event. For other intercurrent events, the while on study intervention strategy is applied. That is, the endpoint is defined as the last observed value at or before the visit of interest before the participant discontinued study intervention.

For the ITT Population, OLE Period Population and LTE Safety Population if patients discontinue the study drug due to an AE, the baseline observation will be carried forward to the corresponding time point for evaluation; if they discontinue originally assigned study drug for any other reason, the last nonmissing observation before discontinuation from the originally assigned drug will be carried forward to the corresponding time point for evaluation.

Randomized patients without at least 1 postbaseline observation will not be included for evaluation apart from patients discontinuing study treatment because of an AE. In the occurrences of intermittent missing observations, the last nonmissing observation will be carried forward.

For the Switcher Population, if patients discontinue ixekizumab due to an AE, baseline observation will be carried forward to subsequent time points; if they discontinue ixekizumab for any other reason, the last nonmissing observation while they are on ixekizumab will be carried forward. In the occurrences of intermittent missing observations, the last nonmissing observation will be carried forward.

An mBOCF analysis will be performed on continuous secondary efficacy, exploratory, and health outcomes variables.

6.3.4. *Modified Nonresponder Imputation (mNRI)*

If any patients missed a visit or discontinued study treatment due to the restriction of coronavirus disease 2019 (COVID-19) in the OLT period for the OLT period population, a multiple imputation (MI) method will be used to impute missing data for each component of JIA ACR30, and JIA ACR30 up to Week 16 will be derived using the MI-imputed components. In the MI analyses, missing data will be imputed to estimate what the observations would have been if the patient had not missed a visit or discontinued due to COVID-19. Specifically, MI is the partial imputation of nonmonotone missing data using Markov chain Monte Carlo method with the simple imputation model, followed by a sequential regression. All other missing JIA ACR30 up to Week 16 due to other reasons will be imputed with NRI.

6.4. Multiple Comparisons/Multiplicity

No multiplicity control measures will be used.

6.5. Patient Disposition

The number of patients along with, ITT, OLE, LTE Safety, OLE switcher, and PTFU populations will be summarized, and a listing of disposition will be summarized.

An overview of patient disposition will be summarized by each treatment period using the appropriate populations.

The following patient disposition summaries will be provided (details of the analysis populations can be found in Section 5.1):

- The number and percentage of patients completing Week 16 of the OLT Period on initially assigned treatment and the number and percentage of patients discontinuing on/prior to Week 16 of the OLT Period, by treatment group and primary reason for discontinuation (Analysis population: ITT Population).
- The number and percentage of Switchers completing the OLE Period or prematurely discontinuing from the OLE Period after Week 16, and primary reason for discontinuation (Analysis population: Switcher Population).
- The number and percentage of patients completing the OLE Period and the number and percentage of patients discontinuing from the OLE Period, by treatment group and primary reason for discontinuation, including classified as Switcher during OLE Period (Analysis population: OLE Period Population).
- The number and percentage of patients completing the LTE Period and the number and percentage of patients discontinuing from the LTE Period, by treatment group and primary reason for discontinuation (Analysis population: LTE Safety Population).

- The number and percentage of patients completing the PTFU Period and the number and percentage of patients discontinuing from the PTFU Period, by treatment group and primary reason for discontinuation (Analysis population: PTFU Period Population).

A by-patient listing will also be provided to include the following information:

- Patient disposition during each period, including the date of randomization at Visit 2, the date of first and last dose on initially assigned treatment during the OLT Period, date/reason of initiation of switch to ixekizumab if any, the date of completion or discontinuation of study treatment, the primary reason for discontinuation of study treatment if applicable and date of study discontinuation, and the time to discontinuation (Analysis population: ITT).

6.6. Patient Characteristics

6.6.1. Demographics and Baseline Characteristics

Demographic variables and baseline characteristics (including baseline clinical measures) will be summarized for ITT, OLE period and Switcher populations.

The continuous variables will be summarized using descriptive statistics, and the categorical variables will be summarized using frequency counts and percentages.

A listing of demographics and patient characteristics will be provided as well.

See [Table RHCG.6.2](#) for the demographic variables to be presented.

Table RHCG.6.2. Patient Characteristics

Variable	Continuous Measure Summary	Categorical / Interval Summary	Subgroup Analysis
Age ^a	Yes		
Age at JIA onset (years) ^e	Yes		
Sex	No	Male, Female	
Race	No	American Indian/Alaska Native, Asian, Black/African American, Native Hawaiian or other Pacific Islander, White, or Multiple	
Country	No	Belgium, Denmark, France, Germany, Italy, Spain, Switzerland, Netherlands, UK	
Height (cm)	Yes	None	
Weight (kg)	Yes	None	
BMI ^b	No	Underweight (<18.5 kg/m ²), Normal (≥18.5 and <25 kg/m ²), Overweight (≥25 and <30 kg/m ²), Obese (≥30 and <40 kg/m ²), Extremely obese (≥40 kg/m ²)	
JIA Subtype	No	ERA, JPsA	Yes
Alcohol use	No	Never, Current, Former	
Caffeine/Xanthine consumption	No	Never, Current, Former	
Tobacco use	No	Never, Current, Former	
Prior biologic JIA therapy ^c	No	Never used, Ever used	Yes
Number of prior biologics for JIA ^c	No	0, 1, 2, >2	
Prior csDMARDs ^j therapy for JIA ^d	No	Never used, Ever used	Yes
Prior nonbiologic (Non-DMARD) therapy for JIA ^d	No	Never used, Ever used	Yes
Number of prior csDMARDs ^j for JIA ^d	No	0, 1, 2, >2	

Variable	Continuous Measure Summary	Categorical / Interval Summary	Subgroup Analysis
Number of non-biologic (Non-DMARD) therapies for JIA ^d	No	0, 1, 2, >2	
Number of active joints	Yes		
Number of joints with limited range of motion	Yes		
Physician's global assessment of disease activity (cm)	Yes		
Parent's global assessment of well-being (mm)	Yes		
Worst joint pain (NRS)	Yes		
CHAQ disability index	Yes		
Pain VAS (mm)	Yes		
hsCRP (mg/L)	No	>3 mg/L or ≤3 mg/L	
hsCRP (mg/L)	Yes		
ESR (mm/hour)	No	>20 mm/hour or ≤20 mm/hour	
ESR (mm/hour)	Yes		
Rheumatoid Factor Positive (RF+)	No	Yes or no	
HLA-B27 positive	No	Yes or no	
Juvenile Arthritis Disease Activity Score-27 (JADAS-27) score	Yes		
Juvenile Spondyloarthritis Disease Activity Index (JSpADA ^{f,g})	Yes		
European Quality of Life -5 Dimensions-Youth (EQ-5D-Y) score (VAS)	Yes		
Leeds Enthesitis Index (LEI) for patients with baseline enthesitis (LEI >0)	Yes		
Total Dactylitic Digit Count for patients with ≥1 Dactylitic Digit	Yes		

Variable	Continuous Measure Summary	Categorical / Interval Summary	Subgroup Analysis
Tender Dactylitic Digit Count for patients with ≥ 1 Tender Dactylitic Digit	Yes		
PASI total score ^f for patients who have baseline psoriatic lesion(s) involving Body Surface Area (BSA) $\geq 3\%$	Yes		
Percentage of BSA for patients who have baseline plaque psoriasis	Yes		
Percentage of BSA category for patients who have baseline plaque psoriasis	No	$<3\%, \geq 3\%$	
Methotrexate (MTX) use at baseline	No	Yes or no	Yes
MTX dose among patients who take MTX concomitantly	Yes		
Sulfasalazine use at baseline	No	Yes or no	Yes
Sulfasalazine dose among patients who take Sulfasalazine concomitantly	Yes		
Previous biologic disease-modifying antirheumatic drugs (bDMARDs)	No	Never used or Ever used	
Previous conventional disease-modifying antirheumatic drugs (csDMARDs ^g)	No	Never used, used 1 therapy, 2 therapies, ≥ 3 therapies	
Concomitant csDMARDs ^h	No	Yes or no	
Concomitant NSAIDs ^d	No	Yes or no	
Concomitant oral corticosteroids	No	Yes or no	
Children's Depression Inventory 2 SR(S) (CDI-2)	Yes		
Children's Depression Inventory 2 SR(S) (CDI-2)	No	$<6, \geq 6$	
Columbia Suicide Severity Rating Scale (C-SSRS) since last assessed	No	Suicidal ideation, Suicidal behavior, Suicidal ideation or behavior	
Tanner Stage Scale	No	Female (Breasts): B1, B2, B3, B4, B5 Male (Genitals): G1, G2, G3, G4, G5 Both (Pubic Hair)	

Variable	Continuous Measure Summary	Categorical / Interval Summary	Subgroup Analysis
		PH1, PH2, PH3, PH4, PH5	
Time since JIA symptom onset ^h (years)	Yes		
Time since JIA diagnosis ⁱ (years)	Yes		
Duration of JIA diagnosis (years) ^e categories	No	0 to <2 years, 2 to <5 years, 5 to <10 years, \geq 10 years	

Abbreviations: BMI = body mass index; CHAQ = Childhood Health Assessment Questionnaire; hsCRP = high-sensitivity C-Reactive Protein; ERA = enthesitis-related arthritis; ESR = erythrocyte sedimentation rate; HLA-B27 = human leukocyte antigen B27; JIA = juvenile idiopathic arthritis; JPsA = Juvenile Psoriatic Arthritis; NRS = Numeric Rating Scale; NSAID = nonsteroidal anti-inflammatory drug; PASI = Psoriasis Area and Severity Index; UK = United Kingdom; VAS = Visual Analogue Score.

- a Age in years will be calculated as length of the time interval from the imputed date of birth (July 1st in the year of birth collected in the electronic case report form (eCRF) to the informed consent date.
- b BMI will be calculated as: $BMI (kg / m^2) = Weight (kg) / (Height (m))^2$.
- c Biologic JIA therapies for example: anakinra, canakinumab, tocilizumab, sarilumab, rituximab, etanercept, adalimumab, infliximab, golimumab, abatacept, secukinumab.
- d Other nonbiologics JIA therapies for example: NSAIDs (including COX-2 inhibitors), analgesics, systemic glucocorticoids.
- e Age at diagnosis in years will be calculated as the time interval from the imputed date of birth (July 1st in the year of birth collected in the eCRF) to the date of JIA diagnosis.
- f For JPsA patients who have this score available.
- g For ERA patients who have this score available.
- h Calculated as: $(date of informed consent - date of JIA onset + 1) / 365.25$
Patients who have a completely missing date of onset will have a missing value for the time since JIA onset, otherwise, "January" and "01" will be imputed for the missing month and day respectively in cases where either date components are missing.
- i Calculated as: $(date of informed consent - date of JIA diagnosis + 1) / 365.25$
Patients who have a completely missing date of diagnosis will have a missing value for the time since JIA diagnosis, otherwise "January" and "01" will be imputed for the missing month and day respectively in cases where for these two date components are missing.
- j csDMARDs include: methotrexate, sulfasalazine (the two most important), leflunomide, cyclosporine, and others rarely used.

6.6.2. Historical Illness and Pre-existing Conditions

Historical illnesses and preexisting conditions will be classified using the latest version of the MedDRA.

Historical illness/condition is defined as the condition/event recorded on the Pre-Existing Conditions and Medical History electronic case report form (eCRF) page or on the Prespecified Medical History eCRF page with an end date prior to the date of informed consent.

A preexisting condition is defined as the condition/event recorded on the Pre-Existing Conditions and Medical History eCRF page or on the Prespecified Medical History eCRF page with a start date prior to the date of informed consent, and no end date (that is, the event is ongoing) or an end date on or after the date of informed consent. Adverse events occurring prior to the date of first study injection will also be reported. Note that, if a preexisting condition worsens in severity on or after the date of informed consent, it will be recorded as an AE on Adverse Events eCRF page from the date of worsening onward.

The following summaries will be provided for the ITT Population:

- The number and percentage of patients with historical illnesses by treatment group and overall, by System Organ Class (SOC) and preferred term (PT).
- The number and percentage of patients with preexisting conditions and adverse events occurring prior to the first dose, by treatment group and overall, by SOC and PT.
- The number and percentage of patients with prespecified medical history (hypertension; diabetes mellitus, Type I; diabetes mellitus, Type II; dyslipidemia; psoriatic arthritis; inflammatory bowel disease [Crohn's disease and uncreative colitis]), by treatment group and overall.

Frequency counts and percentages of patients with selected preexisting conditions will be summarized for the ITT population, and also will be summarized by treatment group using the OLE and the OLE Switcher populations.

For a condition/event that is gender-specific (as defined by MedDRA), the denominator and computation of the percentage will include only patients from the given gender.

By-patient listings of historical illnesses and preexisting conditions, respectively, for the ITT Populations will be provided.

6.7. Treatment Compliance

Study treatment dispensed will be listed (including the CT Lot number) for the Safety Population. Study treatment administration and compliance will be listed for the ITT Population.

Patients will record information in a Study Drug Administration Log (captured in the *Exposure* eCRF page), including the date, time, and anatomical location of administration of investigational product, syringe number, who administered the investigational product, and the reason if the investigational product was not fully administered.

Treatment compliance (%) for each patient will be calculated as:

$$100 \times \frac{\text{Total number of injections administered}}{\text{Total number of injections prescribed}}$$

Number of injections prescribed (that is, expected) can be found in [Table RHCG.6.3](#).

Table RHCG.6.3. Number of Injections Prescribed (Assuming adalimumab responders)

CCI

To calculate the number of prescribed injections:

1. For patients who completed, please refer to [Table RHCG.6.3](#)
2. For adalimumab patients who switch to ixekizumab, refer to Table RHCG.2.2. Schedule of Activities – Open-Label Extension Period of the study protocol
3. For patients who discontinue during the OLT, OLE, and LTE Periods, the number of injections prescribed can be derived from the IWRS study drug dispense dataset.

If the response to the question “Was dose administered?” on the Exposure eCRF page is ‘No’ then treatment compliance will be 0% at respective visit.

A patient will be considered overall compliant for the OLT, the OLE, and the LTE Periods, if he/she is missing no more than 20% of the expected doses, does not miss 2 consecutive doses, and does not over-dose (that is, take more injections at the same time point than specified in the protocol) within the respective study period.

Treatment compliance with investigational product will be summarized for the following periods:

- OLT Period (ITT Population)
- Extension Period (OLE and OLE Switcher populations), and
- LTE Safety Population.

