Habits	X							Including caffeine, alcohol, and tobacco consumption. Assessment only for participants 12 years of age or older.

	Screening	Open-Label Treatment Period						Notes
		V2 Baseline	V3	V4	V5	V6	V7	
Visit No	V1							
Study Week		W0	W2	W4	W8	W12	W16	
Study Days (Approximately)	-42 to -7d	0	14 ± 7d	28 ± 7d	56 ± 7d	84 ± 7d	112 ± 7d	
Vital signs (BP, pulse, body temperature)	X	X	X	X	X	X	X	At baseline (Visit 2, Week 0), BP and pulse measured at least 30 minutes pre- and post-injection. BP and pulse should be measured pre- and post-injection at the other visits.
Inclusion/exclusion criteria	X	X						
Previous JIA therapy	X							
Concomitant medications, including medications for indication	X	X	X	X	X	X	X	
AEs	X	X	X	X	X	X	X	See Section 9.2.2.3 for a complete list of AESIs. IBD events will be adjudicated.
Randomization		X						
Dispense study drug		X	X	X	X	X	X	See Section 7.1, for details.
Administer study drug		X	X	X	X	X	X	Ixekizumab is administered on site Q4W. Adalimumab is administered at home Q2W. For training purposes, the first doses may be administered at the site. See Section 7.1, for administration details.
Clinician Reported Measures								
Joint Assessment	X	X	X	X	X	X	X	
Enthesitis Assessment		X	X	X	X	X	X	It includes LEI and active enthesitis count.
Dactylitic Count		X	X	X	X	X	X	
Physician's Global Assessment of Disease Activity		X	X	X	X	X	X	
Clinical Sacroiliitis		X	X	X	X	X	X	
Back Mobility (Schober's Test)		X	X	X	X	X	X	
Body Surface Area (BSA)		X	X	X	X	X	X	
Psoriasis Area and Severity Index (PASI)		X	X	X	X	X	X	
Columbia–Suicide Severity Rating Scale – Screening	X							Assessment only for participants 7 years of age or older at screening.
Columbia–Suicide Severity Rating		X	X	X	X	X	X	Assessment only for participants 7 years of

Scale – Since Last Assessed								age or older.
	Screening	Open-Label Treatment Period					Notes	
Visit No	V1	V2 Baseline	V3	V4	V5	V6	V7	Baseline laboratory samples should be taken before administration of investigational product.
Study Week		W0	W2	W4	W8	W12	W16	
Study Days (Approximately)	-42 to -7d	0	14 ± 7d	28 ± 7d	56 ± 7d	84 ± 7d	112 ± 7d	
Self-Harm Supplement Form	X	X	X	X	X	X	X	Assessment only for participants 7 years of age or older.
Uveitis Evaluation	X	X	X	X	X	X	X	Active uveitis to be excluded at screening. Investigators will assess if the participant has developed uveitis since last visit.
Patient/Parent Administered Measures								
Childhood Health Assessment Questionnaire (CHAQ)		X	X	X	X	X	X	

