7.2. Method of Treatment Assignment

Participants who meet all criteria for enrollment will be randomized or assigned, as appropriate, to treatment at Visit 2. Participants who are bDMARD-naïve will be randomized to ixekizumab or adalimumab in a 1:1 ratio. At least 20 participants will be randomized to ixekizumab and 20 participants to adalimumab. Randomization will be stratified based on the category of JIA (ERA or JPsA). The remaining participants (approximately 60 participants) who are bDMARD-naïve or bDMARD-IR will be assigned to ixekizumab. In practice, this will be accomplished by randomizing the first 40 bDMARD-naïve participants entering the study according to the ratio and stratification described above, with all the subsequent bDMARD-naïve participants being assigned to ixekizumab.

Assignment to treatment groups will be determined by a computer-generated random sequence using an interactive web-response system (IWRS). The IWRS will be used to assign cartons containing investigational product to each participant. Site personnel will confirm that they have located the correct cartons by entering a confirmation number found on the cartons into the IWRS before dispensing to participants.

In the OLE period, all participants who were receiving ixekizumab in the OLT period will continue to receive ixekizumab for approximately 88 weeks.

Participants receiving adalimumab during the OLT period who did NOT attain a JIA ACR 30 response at Week 16 will be switched to ixekizumab in the OLE period.

Participants receiving adalimumab during the OLT period who did attain a JIA ACR 30 response at Week 16 will be given the option to switch or not to switch to ixekizumab in the OLE period. The decision to switch for participants who achieved a JIA ACR 30 response will be left to the participant/participant's caregiver and investigator. A switch from adalimumab to ixekizumab during the OLE period may also occur at any other visit after Week 16 based on the participant/participant's caregiver and investigator's judgment. All participants who enter into the LTE will receive ixekizumab.

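### SAP 6.7 counts injections prescribed for discontinuers from IWRS dispensing rather than the schedule, which understates compliance for home dosing and may overstate it for on-site ixekizumab

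*SAP*

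**What the plan says.** SAP 6.7 (Treatment Compliance) sets compliance at 100 times "Total number of injections administered" divided by the total prescribed, and equates prescribed with expected: "Number of injections prescribed (that is, expected) can be found in" Table RHCG.6.3. It then gives three rules for the denominator.

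1. Completers: "For patients who completed, please refer to" Table RHCG.6.3, a fixed scheduled count.
2. Adalimumab participants who switch to ixekizumab: the protocol's Schedule of Activities for the OLE.
3. Participants who discontinue in the OLT, OLE or LTE: "the number of injections prescribed can be derived from the IWRS study drug dispense dataset".

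A participant is overall compliant for a period "if he/she is missing no more than 20% of the expected doses", has no two consecutive missed doses and does not overdose. A visit whose Exposure page says the dose was not given scores 0% for that visit.

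Protocol 7.6 measures compliance as injections administered against injections needed. On supply, Protocol 7.2 states: "The IWRS will be used to assign cartons containing investigational product to each participant". On place of dosing, the notes to Table RHCG.2.1 state: "Ixekizumab is administered on site Q4W. Adalimumab is administered at home Q2W". In the LTE, participants who opt for home dosing receive drug only at regular visits, every 12 weeks; the others receive it visit by visit (Table RHCG.2.3).

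**The concern.** Two of the three groups have a denominator built from the schedule. The third, in which poor adherence is most likely, has one built from supply. Dispensed and due can part in either direction.

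- **Drug handed out ahead for home use.** At discontinuation some syringes are dispensed but not yet due. Counting them as prescribed turns them into missed doses.
- **Drug dispensed and given at the same on-site visit.** If the visit does not happen, there is probably nothing to dispense. The missed dose then disappears from the denominator.

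In the OLT and OLE the two arms sit on opposite sides of this split, so their compliance figures could be biased in opposite directions, and neither would be comparable with completers. Items 2 and 3 also overlap: a switcher who later discontinues has two possible denominators and no stated precedence.

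**Working it through.** **The plan's own scheduled count.** The body of Table RHCG.6.3 is redacted, but the SAP Revision History gives 23 ixekizumab injections for the OLE. Every 4 weeks from Week 16 to Week 104 inclusive gives (104 − 16)/4 + 1 = 23. The completer rule is therefore a count of scheduled doses.

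Below, compliance = 100 × administered / prescribed, with one injection per dose. "Prescribed" is either the number dispensed (item 3 read literally) or the number scheduled up to discontinuation.

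**Home dosing, LTE ixekizumab.** LTE doses start at Week 104; Weeks 108 and 112 are regular visits, then Week 120 and every 12 weeks (Protocol 5.1.4, Table RHCG.2.3). Suppose a home-dosing participant takes every dose and stops after the one at Week 120.
- Taken and due: Weeks 104, 108, 112, 116, 120 = 5.
- Dispensed: those 5 plus Weeks 124 and 128 = 7.
- Dispensing denominator: 5/7 = 71%. Schedule denominator: 5/5 = 100%.

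The shortfall shrinks later. Stopping after the Week 240 dose gives (240 − 104)/4 + 1 = 35 taken and 37 dispensed: 35/37 = 95%.

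**Home dosing, adalimumab.** OLT visits fall at Weeks 0, 2, 4, 8 and 12, with dosing every 2 weeks. If the Week 4 visit supplies Weeks 4 and 6, a participant who takes Weeks 0, 2 and 4 and then stops scores 3/4 = 75%, against 3/3 by schedule.

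**On-site ixekizumab.** The OLT and OLE schedules place dispensing and administration at the same visits. Assume that a skipped visit leaves no dispense record.

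| Due | Skipped | Given | Dispensing denominator | Schedule denominator |
|---|---|---|---|---|
| 10 | 3 | 7 | 7/7 = 100% | 7/10 = 70% |
| 12 | 6 (alternate) | 6 | 6/6 = 100% | 6/12 = 50% |

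A dose dispensed but not given still lowers the ratio. With 12 due, 3 skipped and 1 dispensed but not given, it is 8/9 = 88.9% by dispensing and 8/12 = 66.7% by schedule.

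**Effect on the overall-compliant classification.** Take 10 doses, each missed independently with probability 0.3 through a skipped visit, and no overdose. These are illustrative values, not figures from the documents.
- The number of ways to have k misses with no two adjacent is C(11 − k, k).
- No two consecutive misses: sum over k = 0 to 5 of C(11 − k, k) × 0.3^k × 0.7^(10 − k) = 0.028 + 0.121 + 0.187 + 0.125 + 0.033 + 0.002 = 0.496.
- Also at most 20% missed by schedule (k ≤ 2): 0.028 + 0.121 + 0.187 = 0.336.

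On the dispensing denominator the 20% condition is always met here, so 49.6% are overall compliant. On the schedule denominator it is 33.6%, a gap of 16 percentage points. This assumes that consecutive misses are counted from the schedule in both cases.

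**The case against.** The strongest objection concerns what item 3 means. Its wording is permissive, prescribed is glossed as expected, and no document describes the IWRS dataset. A programmer could use IWRS visit records to work out what was due. That stands as a limit on the on-site half of the point: a missing record for a skipped visit is plausible but not documented.

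Several stronger readings are tempting and do not hold.
- **Compliance stays near 100% however many doses are missed.** This needs the undocumented assumption, and applies only to doses lost through skipped visits. It concerns the percentage; the classification also uses the consecutive-dose rule.
- **The rules pass 100% against 38% of participants in the 30% example.** The 38% is the schedule-based 20% condition alone, P(Binomial(10, 0.3) ≤ 2) = 0.383. With the consecutive-dose rule the comparison is 49.6% against 33.6%.
- **A home-dosing LTE participant who stops after one of three dispensed doses scores 1/3.** Compliance is calculated per period, so earlier LTE doses count and the figure is 5/7.
- **The count of important deviations is wrong.** SAP 6.14 uses a threshold of under 80% of assigned doses and refers to a separate plan for the definitions. Nothing ties that count to the SAP 6.7 percentage.

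Missed doses are also recorded elsewhere: in the 0%-at-visit rule, in the listings and in CRF deviation records. Protocol 7.2.1 allows a missed dose to be made up within 5 days, so a skipped visit is not always a missed dose. None of this repairs a ratio of patient totals. Finally, a purely scheduled denominator would count temporary interruptions directed by Protocol 8.1.2 as missed doses. That is fair, and the fix should deal with it.

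**Conclusion.** The inconsistency is real and minor. Item 3 departs from the schedule-based rules for the other two groups and from injections needed in Protocol 7.6.

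The home-dosing understatement follows from the documented supply pattern once dispensed is taken as prescribed. It is largest early in a period (71% in the LTE example) and small later. The on-site overstatement (100% against 70% in the example) also requires that a skipped visit leave no dispense record. Under that assumption and a 30% miss rate over 10 doses, the overall-compliant proportion is inflated by about 16 points, because the consecutive-dose rule still catches some participants.

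A reader should not infer any effect on the trial's conclusions. Compliance is descriptive, the primary analysis uses the ITT population with non-responder imputation, and Protocol 8.2 expects discontinuation to be uncommon. The effect is confined to the compliance summaries and any deviation count that is drawn from them.

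**What to change.** In SAP 6.7, item 3, define injections prescribed for participants who discontinue as those scheduled from the first dose in the period up to the date of treatment discontinuation, using Table RHCG.6.3 and the Schedule of Activities. State that:
- temporary interruptions directed by the protocol are handled the same way as for completers;
- the same rule applies to switchers who later discontinue;
- consecutive misses are counted against the same schedule;
- the IWRS data serve only to reconcile supply.

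The cost is a sentence or two in the SAP and a small programming change. No dose, visit or data collection changes.
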